3.4.2.5.3. Intervention implementation data

Data collection during RACD activities is described below.

Questionnaires and human specimen collection: reactive case detection (RACD)

For all household members and co-worker referrals from forest workers in RACD intervention areas, after obtaining informed consent, a short demographic and malaria risk factor survey will be conducted to obtain information on individuals' occupations, recent forest work or travel, ITN usage, and recent care-seeking behavior for fever. Household members and referrals will be linked to the index case through unique codes in order to facilitate follow-up and allow for statistical adjustments, such as clustering by index case.

In the intervention areas, all patients with a *P. vivax* positive RDT will be given a coded and signed informational letter directing them to the nearest health center of hospital for G6PD testing and follow-up treatment. All *P. vivax* patients will be recorded into a registry and given an identification card for presentation and treatment and follow-up visits.

Sites where interviews occur will be geo-located if all parties agree. VMWs may also obtain contact information from consenting persons to allow for follow-up on positive cases and potential creation of support networks for other HRPs.

3.4.2.6. Data management and analysis

Data will be collected via ODK-based tablet application with internal range checks or paper-based with subsequent double-entry, and will be stored in Microsoft Excel or Access. The number of malaria cases, based on RDT and PCR results, will be mapped by village or sub-village and compared between surveys.

Primary outcomes

Outcome 1: Community-level confirmed *P. falciparum* and *P. vivax* malaria parasite incidence

Data pertaining to this outcome will be analyzed on an intention-to-treat basis at the level of health facility catchment area (randomization unit). Cumulative counts of confirmed malaria cases from the health facility registers over the study period and the previous year will be analyzed in a Poisson or

negative binomial regression model with random intercepts at the health center catchment level and an offset for the estimated population size of the catchment area (from administrative data). The models will include a fixed effect for each study arm and a fixed effect for time period (pre- and post-intervention start). The interaction between these two terms will be the primary effect measure (also known as the difference-in-differences estimator). Pre/post-intervention will be determined as all time periods before the start date of the intervention in the areas considered as being pre-intervention and all time periods after (and including the start date of the intervention in the area considered as being post-treatment).

Outcome 2: Community-level PCR-based *P. falciparum* and *P. vivax* parasite prevalence in sampled villages

The effectiveness of the interventions will be assessed as *P. falciparum* and *P. vivax* prevalence via PCR at end-line (post only) using generalized linear mixed effects models with separate random intercepts to allow for clustering within health center catchments. The binomial distribution will be used to analyze prevalence outcomes (logistic regression). All main analyses will be analyzed as intention-to-treat, and all survey clusters will be analyzed within the intervention group assigned at randomization, regardless of adherence. The primary effect estimate will be evaluated using the fixed effects for RACD. Secondary analyses will include adjustment for age, sex, and other potential confounders, and a per-protocol analysis of the primary effect estimate.

Outcome 3: HS-RDT and RDT-based test positivity rate in village-based and forest-based samples

The HS-RDT and RDT test positivity rate will be estimated for the RACD areas during each intervention. This will be done as soon as data on HS-RDT results are available. Differences in test positivity measures over time and between village and forest base samples will be assessed using a χ^2 test, as well as logistic regression models to account for potential confounding factors.

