Estimated enrollment	
 1) Confirmed case incidence across 32 health center catchment areas: population of approximately 145,000 2) Village-based reactive case detection: estimated 14,400 3) Forest worker reactive case detection: estimated 2,880 4) Endline household survey: 14,080 persons at end-line 5) Qualitative surveys: 6 Focus group discussions (FGDs) and 18 Key informant interviews (KIIs) at baseline, 9 FGDs and 18 KIIs at end-line. 6) Competency checklists with 32 VMWs at baseline, midline, and endline 7) Entomological human landing catches: 20 collectors over three nights at baseline
Statistical and analytical plan	Rapid reporting of microscopy or RDT and HS-RDT positivity will be analyzed as interventions are implemented (or shortly thereafter) to provide preliminary assessment of interventions. Negative binomial (for incidence) and generalized linear mixed effects (for prevalence) models will be used to test the effect of each intervention independently (main effects) relative to control (standard of care). For the enhanced RACD vs. control comparison, both country-specific and pooled analyses will be conducted.

2 Background and introduction

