3.4.2.2. Randomization

A total of 32 health center catchment areas (HCCAs) in Laos will be selected for inclusion based upon incidence per 1000 population between October 2017 and September 2018. HCCAs with higher incidence will be prioritized to improve power; where possible, directly neighboring HCCAs will not both be included to reduce contamination. Restricted randomization of the HCCAs into either RACD or control arms will be conducted, whereby sets of randomizations (with 16 HCCAs in each arm) will be generated that achieve balance across arms on incidence per 1,000 over the prior year, population size, and amount of forest cover. From these sets of potential randomizations, a single randomization will be randomly selected to assign 16 HCCAs each to the RACD or control group. Restricted randomization in this way will ensure balance across intervention and control groups on potential confounding factors. The 'sample' command in Stata v14 (StataCorp, College Station, TX) will be used to implement randomization.

Table 5. Study arms

Study arm	Description	Lao PDR
RACD	Reactive case detection led by VMWs in response to cases in study area HCCA, with follow up testing with HS-RDTs/RDTs in both villages and forest workers; referrals for qualitative G6PD testing for P. vivax cases and 14-day PQ for G6PD non-deficient	16
Control	Standard of care including case management through health facilities and malaria posts/VMWs; village-based RACD conducted by district staff in some areas	16

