3.4.2.4. Sample size

3.4.2.4.1. Confirmed *P. falciparum* and *P. vivax* malaria parasite incidence

Assuming an average baseline transmission of 2.5 per 1000 population per year (all species, from 2017 health system data across study sites and a 50% reduction), an average population of 4000 per health facility catchment, and coefficient of variation of 0.6 (based upon 2017 health system data), in order to detect a 50% reduction in cumulative infection incidence (as measured by routine health system surveillance data over an 18-month period) in a random effects Poisson or negative binomial model, a minimum of 16 randomization units will be required in each study arm. A total of 32 health facility catchment areas will be included in Lao PDR, with 16 allocated each to enhanced RACD and control.

Only health facility catchment areas with at least 3 malaria cases in the past year will be considered for inclusion.

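### The Poisson option for the primary incidence analysis does not allow for catchments changing differently over time; remove it, or add a catchment-by-period effect

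*Protocol*

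**What the plan says.** The incidence model is described in three places in the Protocol.

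- Section 1, statistical and analytical plan: "Negative binomial (for incidence) and generalized linear mixed effects (for prevalence) models will be used to test the effect". Only one family is named for incidence.
- Section 3.4.2.4.1, sample size: the calculation is framed "in a random effects Poisson or negative binomial model", with "an average population of 4000 per health facility catchment, and coefficient of variation of 0.6", a rate of 2.5 per 1000 per year, 18 months of follow-up and 16 HCCAs per arm.
- Section 3.4.2.6, Outcome 1: cumulative counts "over the study period and the previous year will be analyzed in a Poisson or" a second family, which the sentence goes on to describe as a "negative binomial regression model with random intercepts at the health center catchment level and an offset for the estimated population size". Arm and period are fixed effects. "The interaction between these two terms will be the primary effect measure (also known as the difference-in-differences estimator".

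Section 3.4.2.6 gives no HCCA-by-period term, robust variance or rule for choosing between the two families.

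Section 3.4.2.2 fixes restricted randomization, seeking "balance across arms on incidence per 1,000 over the prior year, population size, and amount of forest cover". It dates the incidence used to select HCCAs (October 2017 to September 2018) but not the year used for balancing.

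**The concern.** A random intercept per HCCA looks like the allowance for clustering that a cluster-randomized trial needs. For this contrast under a Poisson model it gives none. The intercept describes how HCCAs differ in level, and the interaction compares changes, so the level drops out. What matters is how much the change in rate varies from one HCCA to the next, and the Poisson model has no term for it.

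If the option were used as written, the standard error would be too small whenever HCCAs change by differing amounts. The trial could then claim a reduction in incidence, on its first-listed primary outcome, more often than the nominal rate allows. The summary names a family that largely avoids this, so the protocol offers an acceptable and a poor model without saying which is primary.

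**Working it through.** The protocol states no alpha, power or error rate for this model, so there is no figure of its own to reproduce. The 16 HCCAs per arm are taken as an input.

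**Inputs from section 3.4.2.4.1.** 4000 people × 2.5/1000 = 10 expected cases per HCCA in the pre-year. Over 18 months under the null, 10 × 1.5 = 15. With 16 HCCAs per arm, the totals are 160 before and 240 after in each arm. Between-HCCA coefficient of variation (CV) is 0.6, so CV² = 0.36.

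**Assumptions.** Two-sided 5%; lognormal HCCA rates with log variance ln(1.36) = 0.307; pre/post log-rate correlations of 0.9, 0.7, 0.5 and 0.3.

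**Step 1: what the Poisson model estimates.** Given an HCCA's two-period total, its post count is binomial with a probability that depends only on arm. The interaction is therefore log(post₁/pre₁) − log(post₀/pre₀) from the arm totals, with SE = √(sum of 1/total). A numerical likelihood fit agreed: with totals of 224 and 199 before and 313 and 290 after, both routes gave −0.0420 with SE 0.1270. The result is exact when the offset is the same in both periods.

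**Step 2: model SE at the planning figures.** √(2/160 + 2/240) = √0.02083 = 0.144.

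**Step 3: actual spread, simple allocation.** Variance = 0.02083 + 4(0.36)(1 − r)/16, where r is the correlation on the natural scale, r = (exp(0.307ρ) − 1)/0.36 for log-scale correlation ρ.

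**Step 4: actual spread, allocation balanced on the same pre-year.** The between-arm difference in log pre-year totals has variance 2(1/160 + 0.36/16) = 0.0575. The post difference has variance 2(1/240 + 0.36/16) = 0.0533. Their covariance is 2(0.36/16)r = 0.045r. With the pre difference held at zero, the variance is 0.0533 − (0.045r)²/0.0575.

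**Step 5: type I error** = 2[1 − Φ(1.96 × 0.144/SD)].

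| ρ | r | SD, simple | Error, simple | SD, balanced | Error, balanced |
|---|---|---|---|---|---|
| 1 | 1 | 0.144 | 5.0% | 0.135 | 3.6% |
| 0.95 | 0.942 | 0.161 | 8.0% | 0.149 | 5.7% |
| 0.9 | 0.886 | 0.176 | 10.9% | 0.160 | 7.8% |
| 0.7 | 0.667 | 0.225 | 20.9% | 0.194 | 14.5% |
| 0.5 | 0.462 | 0.263 | 28.3% | 0.214 | 18.6% |
| 0.3 | 0.268 | 0.294 | 33.7% | 0.225 | 20.9% |

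Simulation with arms within 10% on the same pre-year gave 7.7/14.6/18.7/21.3% for ρ = 0.9/0.7/0.5/0.3. Simple allocation gave 10.6/20.3/27.1/32.7%.

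**Step 6: which column applies.** It depends on the balancing year. If that is the selection year (October 2017 to September 2018) and the analysis pre-year is the 12 months before a June 2019 start (June 2018 to May 2019), they share June to September 2018, 4 months of 12. A simulated illustration with that overlap gave 10/19/26/31%, close to the simple column.

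**Step 7: the negative binomial option.** With one cumulative count per HCCA and period, a negative binomial mixed model under simple allocation rejected 5.8/6.8/7.5% at natural-scale correlations of 0.9/0.6/0.3. A t-test on each HCCA's log change rejected 4.5/5.8/5.8%. In the same runs Poisson rejected 10.2/24.7/30.7% (400 runs each, Monte Carlo SE about 1 to 2 points).

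**The case against.** The best defence is that leaving Poisson or negative binomial open is a common placeholder, settled later by looking for overdispersion, and that an analysis plan not shown here may settle it. Section 1 names one of the two permitted families, and it is the sound one. An ordinary check would also expose the worst cases. At the planning figures, a within-arm heterogeneity test at p < 0.05 flags overdispersion in 33/86/98/100% of simple-allocation runs at correlations 0.9/0.7/0.5/0.3. Switching to an HCCA-level t-test when flagged brings the overall error to 7.6/6.8/5.0/4.6% (5.8/4.4/2.6/2.0% with same-pre-year balancing). This limits the practical harm. But the rule is not in the protocol, and one stated option, followed exactly, gives wrong standard errors.

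A reader might infer more than the documents support:

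- **That the trial has a one-in-three chance of a false result.** That needs Poisson kept regardless of the data, a correlation of 0.3 and simple randomization. Section 3.4.2.2 fixes restricted randomization, so the simple figures are only an upper bound.
- **That the protocol shows the correlation to be low.** It gives no value. The area-wide changes listed in section 5.2 would be absorbed by the period effect. The partner programmes mentioned there, and the rule that "HCCAs with higher incidence will be prioritized to improve power", make a correlation below 1 plausible but do not size it.
- **That difference-in-differences is itself wrong.** It is a legitimate choice. Baseline adjustment is a preference, and it gains nothing if restriction already uses the analysis pre-year.
- **That the problem is certainly worse at Table 1's higher counts.** Larger counts do shrink the Poisson SE, but the size then depends on an assumed post-start rate, so the conclusion does not rest on it.

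**Conclusion.** The point holds for the Poisson option only. At the section 3.4.2.4.1 figures its two-sided type I error is about 8% to 21% with same-pre-year balancing. Roughly half of that, 4% to 10%, would be false claims of benefit, against a nominal 2.5%. The error moves towards 11% to 33% as the overlap between balancing year and pre-year falls away.

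These figures rest on assumed correlations of 0.9 to 0.3, an assumed two-sided 5% level, lognormal rates and an assumed 10% balance limit. The cancellation of the intercept rests on none of these; it needs only the stated model and the same offset in both periods.

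The protocol should be corrected here, since it both permits this model and elsewhere names a better one.

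**What to change.** Align sections 3.4.2.4.1 and 3.4.2.6 with section 1 by deleting the Poisson option and keeping one cumulative count per HCCA and period. Alternatively, require an HCCA-by-period random effect, or an equivalent HCCA-level analysis of change. Fix the choice before outcome data are seen, and state which 12 months serve for balancing and which form the analysis pre-year.

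Optionally, add a supporting model of post-start counts adjusted for log pre-year incidence, with a permutation test over the restricted allocation set. Any efficiency gain depends on the pre/post correlation. An HCCA with no pre-year cases would need a small constant (for example 0.5) before taking logs.

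The cost is wording only; the planned analysis already uses both periods' counts by HCCA.

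### The primary incidence effect subtracts a baseline that randomisation already balances; adjusting for that baseline is more efficient, and one of the two permitted models does not hold its error rate

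*Protocol*

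**What the plan says.** Protocol section 3.4.2.6, Outcome 1, models each catchment's cumulative confirmed cases in two periods, the trial itself and the year before it, with a population offset. Two models are permitted. One is Poisson; the other is a "negative binomial regression model with random intercepts at the health center catchment level". On the fixed part: "The models will include a fixed effect for each study arm and a fixed effect for time period". On the effect: "The interaction between these two terms will be the primary effect measure (also known as the difference-in-differences estimator".

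Section 3.4.2.2 allocates 16 catchments to each arm by restricted randomisation, from a set of allocations "generated that achieve balance across arms on incidence per 1,000 over the prior year, population size, and amount of forest cover". The only dated incidence window there is October 2017 to September 2018. The study starts in June 2019.

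Section 3.4.2.4.1 concludes that "a minimum of 16 randomization units will be required in each study arm". Its inputs are a rate of 2.5 per 1000 per year, 4000 people per catchment, a coefficient of variation of 0.6, 18 months and a 50% reduction. It gives no significance level, no power and no correlation between periods.

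The Protocol summary (section 1) describes the analysis differently: "models will be used to test the effect of each intervention independently (main effects) relative to control".

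**The concern.** Difference-in-differences protects a comparison of groups that may differ at baseline. Here randomisation makes the expected baseline difference zero, and the restriction keeps the realised difference small. The subtraction therefore removes no bias. It imports the variation of the baseline year and ignores the balance that the design has secured.

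With one count before and one after per catchment, the interaction is the between-arm difference in mean log change, so the slope on the baseline log rate is fixed at 1. An adjusted analysis estimates that slope from the same data.

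At stake are power and interval width on the first primary outcome. The validity of the test is also at stake, because the same sentence allows a Poisson model with no term for variation of a catchment between periods.

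**Working it through.** **1. The plan's own figure.** Inputs are from section 3.4.2.4.1; two-sided 5% and 80% power are assumed. Expected cases per catchment over 18 months are 4000 × 0.0025 × 1.5 = 15 under control and 7.5 under intervention.

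n = (1.96 + 0.84)² × [1/15 + 1/7.5 + 2 × 0.6²] / (ln 2)² = 7.85 × 0.92 / 0.480 = 15.03, or 16.03 with one catchment added. Power with 16 is Φ(√(16 × 0.480 / 0.92) − 1.96) = Φ(0.93) = 82%.

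The 16 per arm is thus reproduced by comparing post-period rates, with no baseline term.

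**2. Subtraction against adjustment.** Let vp and vq be the variances of a catchment's observed log rate before and after, and c their covariance.

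- Difference-in-differences: vp + vq − 2c
- Baseline-adjusted: vq − c²/vp
- Excess of the first over the second: (vp − c)²/vp, which is never negative and is zero only if the slope c/vp equals 1.

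On the same inputs the between-catchment log variance is ln(1 + 0.6²) = 0.3075. A baseline year has 4000 × 0.0025 = 10 expected cases, so vp = 0.3075 + 1/10 = 0.4075. Averaged over arms, vq = 0.3075 + (1/15 + 1/7.5)/2 = 0.4075. With ρ the correlation of the true rates, c = 0.3075ρ. Even at ρ = 1 the slope is only 0.3075/0.4075 = 0.75.

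At ρ = 0.5, c = 0.1537:

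- The variances are 0.5075 (difference-in-differences) and 0.3495 (adjusted), a ratio of 1.45. Standard errors with 16 per arm are √(2 × 0.5075/16) = 0.252 and √(2 × 0.3495/16) = 0.209.
- If the allocation forces balance on this baseline, the difference-in-differences estimate varies with the smaller standard error but is tested with the larger. Its error is 2Φ(−1.96 × 0.252/0.209) = 1.8%.
- Its power is Φ((0.693 − 1.96 × 0.252)/0.209) = 83%, against Φ(0.693/0.209 − 1.96) = 91% when adjusted.

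The same formulas give gaps of 25 points at ρ = 0, 17.5 at 0.2, 14 at 0.3, 4 at 0.7 and under 1 at 0.9. Difference-in-differences falls below the post-only comparison when c < vp/2, that is ρ < 0.66.

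**3. Simulated power, cluster-level log-rate t-tests, 50% reduction.** A uses the section 3.4.2.4.1 inputs (1000 trials per cell; allocation from the best-balanced 10% of 200). B uses Table 1 district-average populations, 6.77 per 1000 before, 2.5 per 1000 per year after under control, and CV 0.6 (3000 trials per cell; balance within 10%). C is a separate cluster-level repeat. The tolerances are assumptions, because section 3.4.2.2 gives none. Entries are difference-in-differences against adjusted.

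| ρ | A | B | C |
|---|---|---|---|
| 0.2 | | 64% vs 81% | 63% vs 81% |
| 0.3 | 65% vs 84% | | |
| 0.5 | 72% vs 87% | 77% vs 85% | 77% vs 86% |
| 0.7 | 82% vs 89% | | 89% vs 92% |
| 0.8 | | 93% vs 95% | |
| 0.9 | 92% vs 96% | | 95% vs 96% |

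Ignoring the baseline gave 81 to 82% in B, so at ρ of 0.5 or less the planned contrast was the weaker of the two. If A is given a baseline of Table 1 size (147,798 × 6.77/1000 / 32 ≈ 31 cases per catchment), the gap falls to 12 points at 0.3, 8 at 0.5 and 3 at 0.7.

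**4. Simulated type I error, setting A, nominal 5%.**

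| Analysis | ρ 0.3 | 0.5 | 0.7 | 0.9 | 1.0 |
|---|---|---|---|---|---|
| Difference-in-differences, negative binomial | 2.7% | 2.8% | 3.5% | 5.2% | 3.2% |
| Difference-in-differences, Poisson, catchment intercept only | 23.6% | 17.2% | 15.3% | 8.0% | 3.4% |
| Difference-in-differences, log-rate t-test | 1.7% | 1.5% | 1.5% | 3.2% | 2.2% |
| Adjusted, log-rate t-test | 5.3% | 4.5% | 4.6% | 5.4% | 4.5% |
| Adjusted, negative binomial Wald | 9.3% | 7.3% | 7.1% | 7.6% | 6.8% |

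The negative binomial dispersion absorbs catchment-by-period variation. The Poisson model has nowhere to put it, so its standard error is too small unless ρ is near 1. Without the restriction, the negative binomial difference-in-differences ran at 5.8% (ρ 0.5) and 8.3% (ρ 0.9).

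**The case against.** Difference-in-differences is consistent under randomisation, clearly defined and prespecified. The complaint is efficiency, not bias, and its size rests on a correlation that the protocol does not report. At about 0.7 and above, the contrast matches or beats the unadjusted post-period analysis for which the trial was sized (98% against 94% at 0.9 for the negative binomial versions). The mismatch with section 3.4.2.4.1 therefore does not by itself show an underpowered trial. All of that stands.

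It also stands that the conservatism needs the balanced year to be the subtracted year. Section 3.4.2.2 dates only October 2017 to September 2018. Section 3.4.2.6 refers to the previous year and then to all time before the start. If these are different data, error moves back towards or above 5%. Nor is an adjusted negative binomial Wald test a clean replacement, since it ran at about 6 to 9%.

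What does not stand is that the choice is a matter of taste. Apart from one degree of freedom, adjustment does not lose to subtraction. The protocol also gives reasons not to assume a correlation near 1: section 2.1 reports a recent steep fall in incidence, and section 5.2 expects large changes and shifting forest activity.

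A reader might infer from section 1 that the protocol would test the arm main effect, which in the section 3.4.2.6 model is the pre-intervention difference. The text does not support that. The same summary entry promises country-specific and pooled analyses in a one-country trial, so it reads as wording left from a design with several interventions. It needs editing but is a side point.

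**Conclusion.** The concern holds as a matter of efficiency and model choice. The planned contrast is less efficient than adjusting for the same baseline. The loss is roughly 17 to 19 points of power at a correlation of 0.2 to 0.3, 8 to 15 at 0.5, 3 to 7 at 0.7 and 1 to 4 at 0.9, and at about 0.5 or below the contrast is weaker than ignoring the baseline. These figures rest on cluster-level log-rate tests, CV 0.6, two-sided 5%, an assumed balance tolerance, and balance on the same year that is subtracted.

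Two stronger readings are tempting. One is that the trial loses 17 points of power. That figure belongs to one assumed correlation (0.2), and it is neither a documented value nor a bound. The other is that the test runs below 5% and its intervals are too wide. That is mostly true of the negative binomial or cluster-level version when the balanced year is the pre-period. The Poisson option errs the other way, at about 8 to 24% for correlations from 0.9 down to 0.3. The documents support neither reading as a general statement.

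The change should be made, because it is nearly free and the paragraph as written also leaves open a model that does not control error.

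**What to change.** In section 3.4.2.6, Outcome 1:

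- Make the primary effect the arm rate ratio for the period after the start date, adjusted for the catchment's log baseline incidence rate. Alternatively, keep both periods and constrain the arms to a common baseline mean.
- Fix one baseline window by calendar dates, and say whether it is the year used in the restricted randomisation. The minimum of 3 cases applies to the selection year, so state how a zero count is handled if another window is used.
- Use a test that is valid with 32 catchments: a cluster-level log-rate regression on t with 29 degrees of freedom (32 − 3), or a permutation test within the set of restricted allocations. Do not rely on an uncorrected negative binomial Wald test.
- Remove the Poisson model with only a catchment intercept.
- Keep the difference-in-differences as a sensitivity analysis.

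In section 1, name the same arm effect, and delete the wording on separate interventions and on country-specific and pooled analyses.

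The cost is wording and one degree of freedom. No new data are needed.
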